5.5.1 Handling of Withdrawals

If the participant requests to be withdrawn from the study, they will be given appropriate treatment, but will not continue with scheduled study follow-ups. If the participant withdraws from the study and withdraws consent for disclosure of future information, no further evaluations will be performed and additional data will not be collected. The investigators may retain and continue to use data collected before withdrawal of consent.

5.6 Compensation

5.6.1 Participant Compensation

Participants will be paid up to \$150 for completing the research assessments described in Table 1 (Section 5.0). Payment will be provided on a pro-rated, weighted fashion: \$25 for the Baseline Assessment, up to \$20 for Quarterly Assessments through 12 months. Participants will receive \$10 for the biospecimen collection at baseline, \$15 at 6 months and \$20 at 12 months. Compensation will be distributed to participants by UW research staff unless other arrangements have been made.

5.7 Retention Activities

5.7.1 Maintaining Contact

Participants will be asked to confirm their contact information before beginning each research assessment. They will also be asked to confirm the contact information of family members, friends, and employers who may be asked to update the participant's contact information should they be otherwise lost to follow-up.

6.0 Outcome Assessments

6.1 Primary and Secondary Outcomes

Patient Reported Outcomes (PROs) will be assessed for adults using both generic and disease-specific surveys utilizing the QoL instruments in Table 2.

Table 2. Primary and secondary outcomes and intervention related process measures.

| Primary or Secondary | Name of Outcome | Specific Measure to Be Used | Time Point |
|----------------------|---|--|------------------------|
| Primary | Willingness to enroll | Enrolled/approached | Baseline |
| Primary | Adherence to USDA Med-Style Food Pattern | USDA Med-style Pattern score calculated from the NASR FFQ. ¹⁶¹ | Baseline, 6, 12 months |
| Primary | Participant retention | Proportion enrolled and retained at 3, 6, 9 and 12 months | 3, 6, 9 and 12 months |
| Primary | Interaction with on-line program | Number of times accessed | Bi-weekly |
| Primary | Engagement with nutrition services | Number of sessions with dietician | Quarterly |
| Secondary | Plasma, IL-6, IL-10, IL-1 β , fecal calprotectin | Concentration | Baseline, 6, 12 months |
| Secondary | Diverticulitis events | Self-reported (presumed), subset of those resulting in healthcare utilization (e.g., hospitalization, surgery). | Quarterly |
| Secondary | NSQIP-defined complications, a subset of which are serious adverse events to be reported to ISM | Standardized assessment-serious events defined as death, cardiac arrest, myocardial infarction, pneumonia, progressive renal insufficiency, acute renal failure, pulmonary embolism, deep vein thrombosis, return to operating room, serious site infections | Quarterly |
| Secondary | DVQOL ⁶⁵ | A 17-item questionnaire that assesses four domains: symptoms, concerns, emotions, and behavior changes related to diverticulitis. | Baseline, 6, 12 months |
| Secondary | GIQLI ¹⁵⁹ | A 36-item questionnaire that assesses five domains: gastrointestinal symptoms, physical function, emotional well-being, social well-being, and perception of medical treatment measured by a single item question. | Baseline, 6, 12 months |

| | | | |
|-----------|--------------------------------|--|------------------------|
| Secondary | IPAQ Short Form ¹⁶⁹ | A validated 7-item questionnaire: moderate and vigorous physical activity, walking, and sitting in the past 7 days | Baseline, 6, 12 months |
| Secondary | Time in healthcare | Days missed from work/school, ED/hospital encounters, diverticulitis-related diagnostic/therapeutic interventions | 3, 6, 9 and 12 months |
| Secondary | Self-reported weight | Self-reported weight | Baseline, 6, 12 months |

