4.2 Participant Screening

Patients presenting to University of Washington Medicine gastroenterology and surgery clinics at UWMC and Harborview will be screened, remotely and/or in-person, by the research team. Patient-facing flyers will be posted at the clinic locations to allow potential participants to ask their clinician about the study or to access study information via a link/QR code/study contact information. Patients deemed eligible via initial clinician/research team pre-screening will have eligibility confirmed. They will then be given time to ask questions about the study to determine whether they are interested in participating.

Patients will also be able to begin a self-screening process on the Surgical Outcomes Research Center (SORCE) website, guiding them through simple yes/no eligibility questions to determine if the trial might be right for them (study eligibility from screening form). Patients will have the opportunity to review a consent form but will be contacted by a research team member for a consent call before they are able to sign and provide consent to participate. A study investigator will confirm eligibility before randomization, but no clinic visit will be required of those patients interested in enrolling in this manner. To be considered for participation, patients must have had a confirmed diagnosis of diverticulitis by a physician, with medical records to be accessed by study physician(s) to confirm.

The study team will also contact patients previously seen for diverticulitis and screened for other trials. Basic eligibility information will be visible to the research team through medical record screening.

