5.3 Medical Record Review

Time points

Participants will have their EMR reviewed at ad-hoc time points if triggered by a survey response or if they have a diverticulitis event. Study staff will conduct an EMR review to assess the following:

1. Complications for patients using the National Surgical Quality Improvement Program (NSQIP) definitions and protocol; and
2. The following information related to diverticular disease:
 - a. Indication for healthcare utilization
 - b. Length of stay (if hospitalized);
 - c. Surgery type, if applicable.

As needed, chart review will be conducted if a patient reports an adverse event and further documentation is needed.

Data Collection

Data will be collected using the following forms:

| Form | Description |
|-------------|--------------------|
|-------------|--------------------|

| | |
|-----------------------------|--|
| Form Information | Captures information about when the form was filled out (time point), and by whom |
| Enrollment Form | Completed at index visit only; captures basic demographics and treatment assignment data; medical history and cohort designation |
| Healthcare Utilization Form | Captures information about any visit (date, setting, treatments, medications) |
| Adverse Events Form | Captures information about adverse events at any time point |

If a participant seeks care at an outside hospital, the study team will work with the participant to obtain relevant information.

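### Diverticulitis events are counted on unblinded self-report, and the record review already triggered by each event is not used to confirm or reclassify it

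*Combined protocol and SAP*

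**What the plan says.** Section 6.1, Table 2 makes diverticulitis events a secondary outcome, assessed quarterly and measured as "Self-reported (presumed), subset of those resulting in healthcare utilization (e.g., hospitalization, surgery". That gives two tiers: everything reported, and those reports that led to use of care. The second tier is described by examples only.

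Section 5.3 provides a record check after the event: "Participants will have their EMR reviewed at ad-hoc time points if triggered by a survey response or if they have a diverticulitis event". Among the items abstracted is "Indication for healthcare utilization", with length of stay and surgery type. The Healthcare Utilization Form in the same section is described as "Captures information about any visit (date, setting, treatments, medications"; indication is not among its listed contents. For care elsewhere, "If a participant seeks care at an outside hospital, the study team will work with the participant to obtain relevant information".

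For entry, section 4.2 sets a stricter standard: a "confirmed diagnosis of diverticulitis by a physician, with medical records to be accessed by study physician(s) to confirm".

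Section 8.1 leaves participants unblinded and blinds the investigator team and data-collection staff. Section 8.5 tabulates binary endpoints by arm without naming diverticulitis events. Sections 8.4 and 8.7 rule out formal testing.

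**The concern.** The same disease is held to two standards. To enter, a participant needs a diagnosis verified in the record. To count as an outcome, an episode needs only the participant's report. The record is then opened and the reason for care is abstracted, but the plan gives that information no role in the outcome. A participant who reports an attack, and whose visit proves to be for something else, remains an event in the self-reported tier. That participant also stays in the utilization tier, because a visit did take place.

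Two consequences follow. Reports that are not diverticulitis dilute any difference between arms, because diet has no reason to prevent them. Reporting may also differ by arm: participants know their assignment, and the Mediterranean-style arm has bi-weekly prompts and dietitian contact (sections 4.6, 5.1 and 5.2.2) while the fiber arm has a pamphlet (section 4.7). Without a confirmed tier by arm, neither problem can be seen in the pilot's data. This matters beyond a secondary table because Aim 1 looks ahead to a larger trial focused on recurrence and complications.

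**Working it through.** **Tracing an event through the plan**

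1. A participant reports an episode at a quarterly contact (Table 1, symptoms and healthcare use). It enters the first tier of Table 2.
2. The report triggers a record review (section 5.3). The wording of the trigger treats the event as already established, so the review comes after classification.
3. The indication is abstracted. No section then says that an indication other than diverticulitis removes or relabels the event. There are no diagnostic criteria and no category for confirmed.
4. Section 8.5 does not close the gap, because it neither mentions these events nor chooses a tier.

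**Illustration of what dilution could cost a later trial**

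The plan has no recurrence rate, event count or recurrence power to reproduce; the precision statement in section 8.7 concerns adherence. Every input below is therefore an assumption:

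- Reported rate in the fiber arm: 0.20. Section 2.0 gives at least 20% after a first episode, with no time frame, so using it as a trial rate is an assumption.
- Relative risk on real episodes: 0.7. Two-sided 5%, 90% power, 1:1 allocation.
- Share of reports that are real, v: 0.9, 0.7 or 0.5.
- False reports are equally frequent in both arms, and the confirmed tier finds every real episode.

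Formula, per arm: n = (1.960 + 1.282)² × [p1(1 − p1) + p2(1 − p2)] / (p1 − p2)², with (1.960 + 1.282)² = 10.507 before rounding of the quantiles.

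Self-reported endpoint: p1 = 0.20 and p2 = 0.7 × 0.20v + 0.20(1 − v). Confirmed endpoint: p1 = 0.20v and p2 = 0.7 × 0.20v.

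For v = 0.7:

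- Self-reported: p2 = 0.098 + 0.060 = 0.158; n = 10.507 × (0.1600 + 0.1330) / 0.042² = 1,745.
- Confirmed: p1 = 0.14, p2 = 0.098; n = 10.507 × (0.1204 + 0.0884) / 0.042² = 1,244.

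| Share real | Self-reported rates | Observed RR | n per arm | Confirmed rates | n per arm | Ratio |
|---|---|---|---|---|---|---|
| 0.9 | 0.200 vs 0.146 | 0.73 | 1,026 | 0.180 vs 0.126 | 929 | 1.1 |
| 0.7 | 0.200 vs 0.158 | 0.79 | 1,745 | 0.140 vs 0.098 | 1,244 | 1.4 |
| 0.5 | 0.200 vs 0.170 | 0.85 | 3,515 | 0.100 vs 0.070 | 1,811 | 1.9 |

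Sizes are rounded to the nearest whole number. Within a row the absolute difference between arms is the same for both endpoints, since the false reports cancel. The ratio is the extra variance they add. The comparison is like for like: each self-reported size is set against the confirmed endpoint at the same share of real reports.

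**The case against.** The strongest reply is that this is a descriptive secondary outcome in a feasibility trial of 75 with no formal testing, and that the plan does look at records. Both statements are right. Someone might infer from Table 2 that records go unseen; section 5.3 shows otherwise, and the gap is only that the review is not tied to the outcome. Blinded data collection (section 8.1) also helps, but it cannot blind a participant's own report.

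A reader might also infer that the plan contradicts itself on what healthcare utilization means, because Table 2 mentions hospitalization and surgery, the time-in-healthcare row lists "Days missed from work/school, ED/hospital encounters, diverticulitis-related diagnostic/therapeutic interventions", and the form covers any visit. The documents do not support that. The Table 2 list is one of examples, time in healthcare is a separate outcome, and the form is a collection tool. Whether a clinic visit counts is unclear, but that is an ambiguity, and a clinic-treated attack is in the self-reported tier in any case.

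A third tempting inference is that the recurrence rate could differ several-fold by tier. No split by setting is given, so any such multiple comes wholly from assumed shares. Nor does any section say that the pilot will supply the recurrence rate for the larger trial: section 8.2 lists sites, recruitment and coordinator effort, and section 8.7 speaks generally of effect sizes and variances. With 15 events in 75, the exact 95% interval would be 11.6% to 30.8%, so no tier can fix a later trial's size.

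These replies limit the importance of the point. They do not supply a rule for an event that the record contradicts.

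**Conclusion.** The point stands as a worthwhile improvement to a secondary outcome. The plan collects what is needed to confirm most care-seeking episodes and does not use it to define the outcome. A self-reported tier from unblinded participants is therefore exposed to misclassification and arm-dependent reporting that the pilot could measure.

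The size is unknown from the documents. Under the stated assumptions, relying on self-report would raise a later trial's size by a factor of 1.1 to 1.9 as the share of real reports falls from 90% to 50%. The factor assumes complete confirmation and equal false reporting in both arms; differential reporting would add bias that it does not capture. Nothing here alters the pilot's enrollment of 75, its allocation or any stated precision.

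**What to change.** In Table 2, replace the diverticulitis-events measure with three nested tiers, and name them in section 8.5:

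- (a) any self-reported episode;
- (b) episodes in (a) with care in any setting for which the indication abstracted in the section 5.3 record review is diverticulitis;
- (c) episodes in (b) leading to hospitalization or surgery.

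Report by arm the share of (a) that is confirmed, not confirmed, and with records unobtainable. Name (b) as the tier carried forward when recurrence is described for the larger trial. This also settles whether an outpatient visit counts.

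The cost is mainly wording, since the triggered review already abstracts the indication. There are real limits. Tier (b) will have fewer events than (a), and an attack for which no care was sought cannot be confirmed. Confirmation will be incomplete when care is sought elsewhere, where section 5.3 relies on working with the participant, or when people enrol through the website without a clinic visit (section 4.2). The indication has to come from the record review, because the Healthcare Utilization Form does not list it.

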6.2 Clinical Complications

Death, SAEs, and complications (reported as AEs via EMR review) will be assessed and recorded through the study surveillance period. Complications (reported as AEs) will incorporate NSQIP standards and definitions as well as events related to antibiotic-related complications.

Table 3: Summary of SAE/AEs

| Serious Adverse Events | Adverse event |
|--|--|
| Death | |
| Life-threatening event | |
| CVA or stroke | |
| MI requiring treatment or cardiac arrest | Myocardial infarction Atrial arrhythmia |
| Unplanned admit to ICU | |
| Acute Renal Failure (requiring dialysis) | Major UTI (e.g., pyelonephritis) Urinary retention Acute Renal Failure (no dialysis) Progressive renal insufficiency |
| C. difficile colitis (requiring colon resection) | |
| Pulmonary embolism requiring therapy | DVT/PE requiring treatment |
| Coma >24 hours | |
| Septic shock (requiring pressors) | Sepsis |
| Bleeding requiring transfusion | |
| Newly infected prosthetic graft infection | |
| Mechanical ventilation >48 hours | Tracheal reintubation/tracheostomy |
| Colostomy or ileostomy | NG tube replacement (non-routine) Bowel obstruction Ileus |
| | Organ/space infection (including peritonitis) Surgical site infection Intra-ab Abscess Severe dehydration Hernia Malignant hyperthermia Pneumonia Other infection Other post-op occurrence: unspecified Other non-operative intervention: unspecified Unplanned (re)operative intervention during index C. difficile colitis (not requiring colon resect) |

| | |
|------------------------------|--|
| Other life threatening event | |
| Hospitalization* | |

*Exception to hospitalizations that do not need to be reported as an SAE:

- Planned, elective surgical procedures
- Labor and delivery
- Psychiatric hospitalizations

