4.4 Exclusion Criteria

Participants must not have any of the following exclusion criteria:

1. Unable or unwilling to return for specimen collection visits or be contacted for and/or complete research surveys;
2. Currently incarcerated in a detention facility or in police custody (patients wearing a monitoring device can be enrolled) at baseline/screening;
3. Last episode of acute diverticulitis currently unresolved (i.e., on antibiotics for diverticulitis; drain in place)
4. Intolerance/allergy to the main components of the Med-style food pattern;
5. Surgery for diverticulitis within past 6 months without an episode of diverticulitis post-surgery
6. Planned elective surgery in next 6 months

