5.1 Study Schedule Overview

Consented and randomized participants will be asked to complete research assessments on the topics and at the time points described in Table 1. Research coordinators (RCs) or study team members will offer baseline and follow-up assessments in multiple modalities in order of participant preference (e.g., online, on paper, or over the phone). Participants randomized to the USDA Healthy Med Style food pattern (Medi for All) will receive electronic nudges to support behavior change. Additionally, the study dietitian will provide online group counseling sessions and office hours for participants to schedule individual online follow up counseling sessions which will provide additional content related to wellness, self-efficacy and motivation.

Table 1. Participant Assessment Schedule.

| Item | Baseline | Bi-Weekly | Monthly | Follow-Up Time Point | | | |
|-------------------------------|----------|-----------|---------|----------------------|---|---|----|
| | | | | Month | | | |
| | | | | 3 | 6 | 9 | 12 |
| Contact Information | x | | | x | x | x | x |
| Food Frequency Questionnaires | x | | | | x | | x |
| Online Diet Program | x | x | | x | | | x |
| Blood and Stool Sample* | x | | | | x | | x |
| DVQOL | x | | | | x | | x |

| | | | | | | | |
|--|---|---|--|---|---|---|---|
| IPAQ | X | | | | x | | x |
| Gastrointestinal Quality of Life (GIQLI) ²² | x | | | | x | | x |
| Mediterranean Diet Assessment Score (MEDAS) | | x | | x | x | x | x |
| Adverse Events | | | | x | x | x | x |
| Self-Reported Weight | x | | | | x | | x |
| Diverticulitis Symptoms & HCU | x | | | x | x | x | x |
| Beyond Demographics | x | | | | | | |

*Up to 40 participants will be also invited to submit a stool sample for fecal calprotectin analysis. This will be collected at baseline, 6 months, and 12 months.

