5.2.3 Follow-up Assessments (3, 6, 9, and 12 months)

In-person follow-up assessments will be prioritized around the participant’s clinical appointments. UW study staff will contact the participant to complete assessments prior to their scheduled blood draw/fecal specimen collection. This outreach will include a combination of phone, mail, and email as determined by the contact information provided by the participant. If a participant hasn’t completed their scheduled follow up assessment at the time of their visit, the study staff will attempt to complete it in person. The follow-up assessments are listed in detail in Table 1.

In addition to the survey assessments, participants’ specimens will be collected at 6 and 12 months following the same guidelines as in the baseline visit. Specimen collection will coordinate with clinical appointments whenever possible.

See section 5.2.1 for specimen collection instructions, which remain the same for follow-up time points. Participants will be reminded that they are welcome to contact their research coordinator at any time if any questions or concerns should arise. UW study staff will communicate with the research coordinator to ensure appropriate reporting is completed should an AE or complication be reported to them.

Self-reported complications or AEs will be recorded. Any serious adverse events (SAEs) will be communicated to the relevant site study team to ensure appropriate reporting is completed.

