8.5 Secondary Statistical Analyses

Binary and categorical endpoints (e.g., adverse events and complications) will be tabulated by intervention group. Time in healthcare will be summarized by group using medians and interquartile ranges, and differences between intervention groups will be summarized using 95% confidence intervals generated from generalized linear regression models appropriate for each type of outcome (e.g., binary, count, continuous, etc.). To examine the sensitivity of adherence to the Med-style Food Pattern on changes in serum biomarkers, we will modify the primary analytic model described for Aim 2 by separately adjusting for a binary indicator of adherence (adherent vs. not) and a graded measure of adherence to intervention. Finally, we will use

mediation analyses to explore the extent to which changes in serum biomarkers over time are mediated through intervention-induced changes in weight and physical activity.

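### The adverse-event list in section 6.2 and Table 3 has no category for non-serious diet intolerance or food reactions, and the plan does not say how self-reported events outside the list are coded

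*Combined protocol and SAP*

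**What the plan says.** **Classification.** Section 6.2 says: "Complications (reported as AEs) will incorporate NSQIP standards and definitions as well as events related to antibiotic-related complications". Table 3 then lists terms such as surgical site infection, tracheal reintubation, malignant hyperthermia, prosthetic graft infection, sepsis and C. difficile colitis. It also lists bowel obstruction, ileus and severe dehydration. Its catch-all entries cover infections, post-operative occurrences, non-operative interventions and life-threatening events.

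**Source.** Section 6.2 also says: "Death, SAEs, and complications (reported as AEs via EMR review) will be assessed and recorded through the study surveillance period". On the timing of that review, section 5.3 says: "Participants will have their EMR reviewed at ad-hoc time points if triggered by a survey response or if they have a diverticulitis event". It adds that charts will be checked as needed when a reported adverse event requires more documentation.

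**Self-report.** Table 1 schedules an adverse-event assessment at months 3, 6, 9 and 12. Section 5.2.3 says: "Self-reported complications or AEs will be recorded". The Adverse Events Form in section 5.3 is described in general terms: "Captures information about adverse events at any time point".

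**Analysis.** Section 8.5 says: "Binary and categorical endpoints (e.g., adverse events and complications) will be tabulated by intervention group".

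**Recognition of the risk.** The fourth exclusion criterion in section 4.4 is: "Intolerance/allergy to the main components of the Med-style food pattern". Section 12.0 names privacy, confidentiality, burden and specimen collection as the main risks, and no diet-related harm.

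**The concern.** Neither arm gives an operation or an antibiotic as the study intervention. One arm receives a diet programme with dietitian support and an offer of olive oil (sections 4.6, 5.1 and 5.2.1). The other receives a pamphlet recommending at least 25 g of fiber a day (section 4.7). The non-serious harms such interventions could plausibly cause are bloating, abdominal pain, altered bowel habit, food reactions and unintended weight loss. The protocol treats known intolerance or allergy as a reason not to enrol someone, but names no AE term for the same problem arising after enrolment.

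Two things are at stake.

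- **Harm reporting.** The pilot could report few diet-related AEs without having systematically asked about them, and the larger trial it is meant to inform could inherit the same list.
- **Interpretation of feasibility.** Adherence and retention are primary outcomes in Table 2. Poor tolerability is a plausible cause of failure on either, and a pilot should be able to identify it.

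**Working it through.** The plan states no figure on this point, so there is none to reproduce. The check is a reading of the capture route, followed by arithmetic for scale.

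**Step 1. Follow a non-serious food reaction or new bloating, first noticed between baseline and month 3, through the plan.**

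| Stage | Where | What happens |
|---|---|---|
| Reported by the participant | Table 1; 5.2.3 | Recorded if mentioned at the month 3 AE assessment. The wording of the question is not given. |
| Entered on a form | 5.3 | The form is general. No categories are shown. |
| Checked in the chart | 5.3; 6.2 | Review is ad hoc. A mild reaction that led to no care may have left no entry. |
| Classified | 6.2; Table 3 | It is neither an NSQIP nor an antibiotic-related complication. No named row fits, and none of the catch-alls covers it. |
| Tabulated by arm | 8.5 | AEs are tabulated, but no category is defined for this one. |

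The event can therefore enter the database. What is undefined is whether it counts as an AE when the chart is silent, and under which heading it is tabulated.

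**Step 2. Check whether other data fill the gap.**

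- *Serious reactions:* covered. Section 9.2 and Table 3 count hospitalization (three exceptions) and life-threatening events as SAEs.
- *Gastrointestinal symptoms and weight:* partly covered. GIQLI and self-reported weight are collected at baseline, 6 and 12 months, and section 8.4 models patient-reported outcomes between arms. These are analysed as outcomes, and weight change also as a mediator (section 8.5), not as harms.
- *Participants who leave:* weakly covered. Section 5.5 allows withdrawal for following a conflicting diet, and under section 5.5.1 a participant who asks to withdraw has no further scheduled follow-up. Someone who cannot tolerate the diet may be gone before month 6.
- *Reluctant participants:* section 5.2.7 gives priority to diverticulitis symptoms and the food frequency questionnaires. It does not name the AE item.
- *Non-serious food reactions:* no named item was found.

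**Step 3. Compare contact between arms.** The Mediterranean-style arm has bi-weekly prompts, outreach when a prompt is missed, and dietitian sessions (sections 5.1 and 5.2.2). The fiber arm has a pamphlet. Without fixed wording, volunteered events may differ between arms because of contact alone.

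**Step 4. Scale.** Arm sizes are n = 50 and n = 25 (section 8.7). The event rates p are assumptions, and full follow-up is assumed. The expected count is n × p, and the probability of at least one event is 1 − (1 − p)^n.

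| Assumed 12-month risk p | Expected, n = 50 | P(at least one), n = 50 | Expected, n = 25 | P(at least one), n = 25 |
|---|---|---|---|---|
| 2% | 1 | 0.636 | 0.5 | 0.397 |
| 5% | 2.5 | 0.923 | 1.25 | 0.723 |
| 10% | 5 | 0.995 | 2.5 | 0.928 |
| 20% | 10 | >0.999 | 5 | 0.996 |

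If no events are seen, the one-sided 95% upper bound on the risk is 1 − 0.05^(1/n): 5.8% for n = 50 and 11.3% for n = 25. Those bounds mean something only if every participant was asked.

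**The case against.** A reader might infer that the by-arm harm table cannot show diet-related harms, or that it will be almost empty however the diets are tolerated. The documents do not support that.

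- AEs are assessed every quarter, self-reports are recorded, and the AE form is not restricted to the NSQIP list.
- Section 8.5 does not limit tabulation to Table 3 terms, and no section says that Table 3 is the complete coding set.
- Bowel obstruction, ileus and severe dehydration are listed.
- Many of the other rows suit recurrent diverticulitis and its treatment. Section 2.0 puts recurrence at 20% or more after a first episode, and Aim 1 looks ahead to a trial of recurrence and complications. The list has a purpose and should stay. Confining it to operated or hospitalised participants would lose outpatient events such as deep vein thrombosis or pneumonia.

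The AE form and quarterly question are described but not reproduced, so they may already contain free text or a field for other events. The rates in the scale calculation are assumptions. They show that common events would occur in samples of this size, not that the plan would miss them.

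Two cautions about remedies also stand. Participants know their arm (section 8.1), so asking whether the diet caused a symptom invites biased answers. Section 5.2.7 already warns of survey burnout.

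These arguments limit the consequence but do not supply the missing category or coding rule. Nor do they reconcile section 6.2 with section 5.2.3.

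**Conclusion.** The point holds as a gap in classification and ascertainment. Section 6.2 and Table 3 have no category for non-serious diet intolerance or food reactions and no general row. The plan does not say how self-reported events outside the list are coded, and sections 6.2 and 5.2.3 give different AE sources without connecting them. Such harms may therefore be missed or left unclassified by arm. It does not follow that they must be.

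The number of events affected cannot be calculated from the documents, because neither a rate nor the wording of the AE question is given. Under assumed risks of 5% to 20%, 2.5 to 10 events would be expected in the larger arm and 1.25 to 5 in the smaller. These would be enough to describe if they were asked about and coded. The conclusion assumes that the unseen AE form has no diet-specific items or general field. If it has, what remains is to state the coding rule and align Table 3. This is a low-cost improvement worth making in a pilot whose purpose is to prepare a larger trial.

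**What to change.** 1. **Table 3.** Keep the existing list. Add a diet-related group: new or worse bloating, abdominal pain or bowel-habit change; food reaction or allergy; unintended weight loss; stopping a food group because of symptoms. Add a general row for any other AE.
2. **Quarterly assessment.** Ask these items in identical wording in both arms at the existing month 3, 6, 9 and 12 AE assessment. Do not ask participants whether the diet was the cause.
3. **Sections 6.2 and 5.2.3.** Reconcile them so that every self-reported AE is coded, whether or not a chart entry exists. Chart review then serves as supporting documentation.
4. **Section 8.5.** State that all coded AEs, including the new group and the general row, are tabulated by arm.

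The cost is a few more survey items, a table shell and more minor AEs to record. The survey burden is real given section 5.2.7, so the items should be short. No visit, sample or change to either intervention is needed.
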